try to contact alters, nor incentivize enrollment with alternative forms of assessment (e.g., phone, home visit, etc.). In the proposed study, we will have resources to hire staff to focus on alter interviews, and to make multiple call attempts, interview alters by phone, reimburse alters for transport, and travel to interview alters outside of Kampala; plus, unlike in the pilot, in the proposed study when an alter is unable to be reached, we will ask the index participant to refer additional alters for us to contact. With these changes, we expect a much higher rate of alter recruitment in the proposed study; nonetheless, our recruitment and power analysis procedures accounted for a potential 50% enrollment rate of referred alters.

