Summary of Preliminary Studies. The team is well-positioned to conduct this RCT, with a great deal of expertise in the proposed study content and methods, and the demonstrated feasibility, acceptability, and preliminary efficacy of *Game Changers*. Based on our pilot, we changed intervention content and methods for the proposed RCT, some of which we already tested for feasibility with the pilot wait-list control group. As requested by pilot participants in the post-intervention focus groups, we added content, practice, and

instruction on social network mapping and more opportunity for prevention advocacy practice (e.g., role plays on HIV stigma and pre-and post-HIV testing support). We also added content related to PrEP (e.g., information about PrEP, and role plays and strategies about how to do prevention advocacy around PrEP), given increased availability in Uganda, especially for key and priority populations (e.g., sero-discordant couples). However, since PrEP access is still limited and not available for all, we will examine it as a secondary outcome only. As noted above, we will modify alter methods, to employ more staff to track alters, ask staff to travel to alters who live away from Kampala, and provide a higher incentive (e.g., for transportation costs); we will also conduct interviews with alters by phone. These revised procedures should decrease the number of alters who decline (or who are not referred) because they live far away or are too busy to come to the site (~20% of the alters referred in the pilot). Nonetheless, we will plan for a 50% alter enrollment rate and ask PLWH to refer up to 7 alters (up from 3 in the pilot), with a target of enrolling an average of 3.5 (and no more than 4/participant).

Study Methods

[figure not shown]
Setting. The study will be conducted at IDI, which provides outpatient HIV care to ~8,000 active patients and conducts HIV-related clinical trials. Luganda is the native language, but people with a secondary education often speak English, and all clinic staff are fluent in English.

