
Randomized Controlled Trial of *Game Changers*

Overview. The proposed design is an individually randomized group-treatment trial using a clustered design.⁹⁶ We will recruit 210 PLWH and randomize 105 to the intervention and 105 to a no-intervention control arm. Each PLWH will be asked to recruit social network members (alters to whom they have disclosed) (736 total, 368/arm). All participants will complete assessments at baseline, and 6, 12 and 18 months post-baseline to assess improved HIV prevention behaviors within the network, mediators of improved behaviors, and HIV outcomes. Participants will be divided into 7 cohorts of 30 (within each cohort, 15 intervention and 15 control). Intervention implementation for the 7 cohorts will be staggered, such that two will be conducted at a time (i.e., 60 PLWH and 210 alters for two cohorts at a time), except the last wave in which there will be one cohort of 30. [name] will oversee the implementation of the intervention program, while [name] will oversee the assessment, data collection and analysis components of the trial.

Randomization. A blocked 1:1 randomization design with stratification by gender (with randomly alternating blocks of 2, 4, and 6 to prevent anticipation of condition) will ensure balance across arms. All groups will be mixed sex (with approximately equal numbers of men and women/group), and a male and a female facilitator will conduct each group. The statistician will use a random number generator to devise a randomization log and a set of sealed numbered randomization envelopes (to prevent condition foreknowledge). After completing the baseline survey, the interviewer will open the corresponding envelope and record the condition. Although individual randomization entails contamination risk, this type of group intervention—where recipients attend several sessions that use structured content and group interaction to target multiple aspects including internalized stigma, comfort and skills with disclosure, and how and who to engage in advocacy with—is less conducive to contamination. Statistical models suggest $\geq 30\%$ of the control arm must receive the equivalent of a full-strength intervention to result in meaningful contamination,⁹⁷ so with a

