To recruit alters, during the baseline social network assessment (see below), we will elicit the names of 20 alters in the PLWH's social network, and ask PLWH to identify alters who know their serostatus. In our prior studies, 87% were able to list 20 alters, and 96% were able to list at least 16 alters. At the end of the interview, PLWH will be asked to select, from the list of alters who know their serostatus, up to 7 alters whom they would be willing to refer to the study; this should be feasible, as the pilot revealed that an average of 13 of the 20 alters knew the participant's HIV status. If they refer more than 4 alters, we will randomly select 4 to target for recruitment (to limit selection bias), although we aim to recruit an average of 3.5 alters per index participant, given that we do not expect to be able to recruit 4 alters from all participants. The decision to recruit 4 is based on a need to balance interviewing enough alters to be sufficiently representative of the person's network, while also being feasible to collect the data from the large sample of overall alters in a longitudinal design. We will request that the PLWH call each selected alter at the end of the interview, and to describe the study opportunity in the presence of the interviewer, who can then immediately schedule a study visit. If any of the 4 refuse to participate or cannot be reached, we will randomly select additional alters on the list of those referred from the index participant until 4 have agreed and enrolled; if only 4 were referred, we will ask the PLWH to refer additional alters, if possible. To enhance alter enrollment, we will allow for phone-based interviews and for staff to travel to meet alters outside of Kampala after the first study visit, and provide a sufficient incentive to cover transport costs; nonetheless, our request for index participants to refer up to 7 alters allows for a 50% alter enrollment rate, in order to achieve our goal of enrolling 3.5 alters per index participant. Given the large number of alters (105/cohort; 210 for two cohorts at the same time), alters will be interviewed over a 2-month period (~25-30 alters per week) at baseline and follow-up. We used similar procedures successfully in our pilot.

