
PROTECTION OF HUMAN SUBJECTS

1. Characteristics of Participants

We will recruit 210 people living with HIV (PLWH) and randomize 105 to the intervention and 105 to the no-intervention control arm. Each PLWH will be asked to recruit up to 4 social network members (alters) to whom they have disclosed (736 total (allowing for average of 3.5 recruited per index participant), 368/arm). Eligibility Criteria for PLWH include (1) ≥18 years-old; (2) in care for > 1 year (because they are more likely to be medically stable, adjusted to their HIV diagnosis, and have disclosed to several people, and thus more likely to be ready to engage in advocacy); and (3) disclosed their HIV status to at least one person. Eligibility Criteria for Alters include (1) ≥18 years-old; (2) referred by a PLWH enrolled in the study; (3) know the PLWH's serostatus; and (4) willing/able to do the first study visit in person. (Other alter study visits can be done by phone, or interviewers can travel to meet alters.) PLWH will be asked to refer at least 7 alters for participation in assessments, in order to ensure enrolling up to 4 alters.

2. Sources of Materials

The data sources in need of safeguarding include self-report survey and social network data (collected at baseline, and 6-, 12-, and 18-months post-baseline); chart abstracted medical data; audio-recordings of intervention sessions; and facilitator, supervisor and participant ratings of intervention sessions. Data for the cost analysis (e.g., study staff documentation of time and resources for intervention activities) will be collected but are not considered to be human subjects data.

3. Potential Risks to Participants

Psychological distress: Distress may result from issues raised during intervention sessions, such as sharing stories about HIV stigma.

Breach of confidentiality: Violation of participant confidentiality is possible, but we believe the safeguards that we have integrated into the study methodology, as described below, will effectively limit this risk.

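### Seven referrals at 50% enrolment yield about 3.2 alters per PLWH (about 673), not 3.5 (736), once the plan's own cap of 4 is applied

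*Combined protocol and SAP*

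**What the plan says.** The Summary of Preliminary Studies sets the rule: "we will plan for a 50% alter enrollment rate and ask PLWH to refer up to 7 alters (up from 3 in the pilot". The same sentence then fixes a mean yield of 3.5 alters and a ceiling of 4 for each PLWH. The Recruitment section repeats the logic: "our request for index participants to refer up to 7 alters allows for a 50% alter enrollment rate, in order to achieve our goal" (the goal being a mean of 3.5). The pilot RCT section says that "our recruitment and power analysis procedures accounted for a potential 50% enrollment rate of referred alters". With 210 PLWH, this becomes 736 alters (368 per arm), and Statistical Power starts from that number.

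The documents differ on how many referrals are requested. The Summary of Preliminary Studies and Recruitment make 7 the maximum. Protection of Human Subjects, section 1, makes it the minimum: "PLWH will be asked to refer at least 7 alters for participation in assessments".

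There are two top-up provisions. The pilot RCT section says that an index participant will be asked for further names when an alter cannot be reached. Recruitment says that further names will be requested, if possible, when only 4 were referred.

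The Summary of Preliminary Studies expects phone interviews and staff travel to reduce the number of alters who decline, or are not referred, because they live far away or are busy. Eligibility criterion (4) for alters requires the first visit in person. Recruitment allows phone interviews and "for staff to travel to meet alters outside of Kampala after the first study visit".

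**The concern.** Multiplying 7 by 50% gives the average number of willing alters, not the average number enrolled. A PLWH with 5, 6 or 7 willing alters contributes only 4, and that lost surplus cannot make up for a PLWH with 0 to 3. The cap therefore pulls the mean below 3.5 even if every PLWH refers the full 7. The 50% scenario is offered as the safeguard for the sample size, so it should deliver 736 under the rules as written.

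The second difficulty concerns the means of raising enrolment above the pilot's level. Two of the named measures start only after a visit that the alter must already have attended.

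At stake are the number of alters available for the two alter-reported primary outcomes, HIV testing and condomless sex, and the accuracy of the statement that recruitment and power allowed for 50% enrolment.

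**Working it through.** **Inputs.** 210 PLWH (Overview of the trial). 7 referrals, 50% enrolment, target mean 3.5 and cap 4 (Summary of Preliminary Studies; Recruitment). 736 alters (Overview; Protection of Human Subjects). 15% attrition leaving 625, effective sizes 612 (ICC .01) and 568 (ICC .05), and a control rate of 65% (Statistical Power). Pilot: 89 of 98 PLWH referred anyone. Of 117 eligible alters, 34 were not reached and 57 enrolled.

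**The plan's figure.** 7 × 0.50 = 3.5, and 3.5 × 210 = 735, against 736 stated. It reproduces, but only without the cap.

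**With the cap.** Let X be the number willing among 7, X ~ Binomial(7, 0.5). The counts out of 128 for X = 0 to 7 are 1, 7, 21, 35, 35, 21, 7, 1.

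- E[min(X, 4)] = (1×7 + 2×21 + 3×35 + 4×64)/128 = 410/128 = 3.203
- P(X > 4) = 29/128 = 22.7%; P(X < 4) = 64/128 = 50%
- Lost to the cap: (1×21 + 2×7 + 3×1)/128 = 38/128 = 0.297, and 3.5 − 0.297 = 3.203
- Enrolled: 210 × 3.203 = 673, which is 8.6% below 736
- Month 18: 673 × 0.85 = 572, against 625

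**Sensitivity** (cap of 4 throughout).

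| Scenario | Mean per PLWH | Total |
|---|---|---|
| 7 referrals, 50% | 3.20 | 673 |
| 7 referrals, pilot rate 57/117 = 48.7% | 3.14 | 660 |
| 7 referrals, 50%, 9% of PLWH refer nobody (× 89/98) | 2.91 | 611 |
| 7 referrals, 50%, within-PLWH correlation 0.1 (assumed) | 3.05 | 641 |
| 8 referrals, 50% | 3.45 | 725 |
| 9 referrals, 50% | 3.63 | 763 |

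Solving E[min(X, 4)] = 3.5 with 7 referrals gives an enrolment rate of 57.2%.

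**Effect on power.** The design effect is 1 + (m − 1) × ICC, with m the retained alters per PLWH. For 625 alters, m = 625/210 = 2.98 and the effective sizes are 613 and 569, matching the stated 612 and 568 to within rounding. For 572, m = 2.72 and they are 562 and 527. With a control rate of 65%, 80% power and the standard two-sided formula for two proportions, the detectable difference moves from 11.1 to 11.6 points (ICC .01) and from 11.5 to 12.0 points (ICC .05). The protocol's own 10.3 and 10.7 points do not reproduce with this formula. That is a separate matter, so both sides of the comparison here use the same formula.

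**Timing of the aids.** The Summary of Preliminary Studies counts phone interviews and staff travel as reducing refusal and non-referral. The eligibility criteria and Recruitment make both available only after the in-person first visit. An alter who cannot attend that visit is ineligible before either can be used.

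**The case against.** The strongest reply is that the list of 7 is not closed. The top-up provisions add names. At pilot rates, replacing each unreached alter once raises the rate per referral slot to 0.487 + 0.291 × 0.487 = 62.9%, a mean of 3.68 and about 773 alters. Replacing half of them gives 55.8%, 3.45 and about 724. The minimum of 7 in Protection of Human Subjects would also permit 8 or 9 referrals. In addition, the pilot's alter recruitment was added post hoc without funding. Dedicated staff, repeated calls, transport money and the PLWH's own call in the interviewer's presence all act before enrolment.

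Much of this stands: 736 may well be reached. It does not rescue the stated justification, which is that up to 7 referrals suffice at 50%. The top-ups carry no number. In Recruitment they are conditional, and stated only for the case of exactly 4 referrals.

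On the aids, knowing that three of the four assessments can be done by phone or by a staff visit might persuade a busy alter to join. That is fair, but it does not help someone who cannot make the first visit.

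Two stronger readings are tempting. A reader might infer that a shortfall in alters weakens every primary outcome. Enacted stigma, however, is measured from PLWH reports on their named network members (Network Composition), so alter enrolment does not set that sample. A reader might also infer that distant alters will be under-represented. The documents give no enrolment figures by distance, so this cannot be shown.

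**Conclusion.** The point holds as a correction to the recruitment arithmetic and to the timing of two aids. Under the rule as justified, the yield at 50% enrolment is about 673 alters (572 at month 18), not 736 (625). This assumes that every PLWH refers exactly 7, that alters enrol independently, and that no top-ups occur. Fewer referrals or clustered refusals lower it; top-ups or a higher enrolment rate raise it.

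The loss is about 0.5 percentage points of detectable difference. It would be about 1 point if 9% of PLWH refer nobody (611 × 0.85 = 519 at month 18). It bears on HIV testing and condomless sex as reported by alters. It does not show that the trial will miss 736 or is materially underpowered. It shows that the safeguard offered for 736 does not work as written and should be corrected.

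**What to change.** 1. In the Summary of Preliminary Studies, Recruitment and Statistical Power, restate the 50% scenario with the cap: about 673 enrolled and about 572 at month 18, with the detectable difference to match. Alternatively, keep 736 and say that it requires about 57% enrolment from 7 referrals, or about 8 to 9 referrals per PLWH at 50%, counting top-ups.
2. Reconcile the maximum of 7 (Summary of Preliminary Studies, Recruitment) with the minimum of 7 (Protection of Human Subjects), choosing a number that supports 3.5 under the cap. Apply the top-up request whenever the referred list runs out before 4 have enrolled, not only when 4 were referred.
3. Reword eligibility criterion (4) and Recruitment so that the in-person first visit may take place where staff travel to the alter.

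The cost is protocol wording, a less favourable 50% figure if the first option is taken, and some extra baseline travel of a kind already planned for follow-up. The way alters are sampled from the network list need not be redesigned.

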multi-component, multi-session intervention like Game Changers it is highly unlikely that casual communication between intervention and control participants could result in meaningful contamination. We will assess and control for whether control participants communicated with intervention peers about intervention content.

Eligibility Criteria for PLWH include (1) ≥ 18 years-old, (2) in care for > 1 year (because they are more likely to be medically stable, adjusted to their HIV diagnosis, and ready to engage in advocacy), and (3) disclosed their HIV status to at least one person. All PLWH also will be patients at IDI's clinic, where they will be recruited. Clients will be excluded if they participated in the intervention as part of the prior R34 pilot study.

Eligibility Criteria for Alters include (1) ≥ 18 years-old; (2) referred by a PLWH enrolled in the study; (3) know the PLWH's serostatus; and (4) willing/able to do the first study visit in person. (After initial screening/baseline visit, other alter study visits can be done by phone, or interviewers can travel to meet alters.) As described below, PLWH will be asked to recruit up to 4 alters for participation in assessments.

Recruitment. As in the pilot, to recruit PLWH: (1) clinic staff and expert patients (who work with clinic staff to track patients) will refer eligible patients to interviewers, who will be in the waiting area of the clinic on weekdays (M-F) every day during the recruitment period for each cohort; and (2) interviewers (who will be IDI staff) will approach all patients in the waiting area on the same designated days, to inform them of the study. Interviewers will cross-check the names of referred patients with IDI clinic records to verify that they are patients at IDI who have been in care for > 1 year and disclosed to at least one person. In the pilot, only one person was screened ineligible due to the disclosure criterion. Because we will enroll two intervention-control cohorts at a time, we need to recruit 60 participants at a time (30 per cohort) or per wave of recruitment; each wave of recruitment will take place over 3 months (30 PLWH and 105 alters enrolled and surveyed per month, 1.5 PLWH and 5-6 alters per day), followed by a 3-month period when the intervention and attention control program are implemented with the two cohorts, and no further recruitment until the next wave of recruitment in the next quarter (see Timeline).

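### On the natural reading, a participant's allocation envelope is opened before that participant's network members attend and give baselines; the order of steps is not stated and the staff handling network members are not said to be unaware of arm

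*Combined protocol and SAP*

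**What the plan says.** The Randomization section describes sealed, numbered envelopes and then states: "After completing the baseline survey, the interviewer will open the corresponding envelope and record the condition". PLWH are the unit randomised (105 per arm), and alters take the arm of the PLWH who referred them.

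The alter paragraph of the Recruitment section sets out these steps:

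- PLWH list 20 network members during the baseline network assessment. At the end of the interview they name up to seven who know their serostatus.
- If more than four are named, four are drawn at random, with limiting selection bias given as the reason.
- The PLWH is asked to "call each selected alter at the end of the interview, and to describe the study opportunity in the presence of the interviewer". Visits can be booked on that occasion.
- An alter who refuses or cannot be reached is replaced at random from the same PLWH's list. A PLWH who named only four is asked for more names.

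The pilot account under Preliminary Studies adds that, in the new trial, the PLWH will be asked for further alters when one cannot be reached. It does not limit this to PLWH who named four.

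Alters must be "willing/able to do the first study visit in person" (Eligibility Criteria for Alters). On staffing, the plan says "we will have resources to hire staff to focus on alter interviews" (Preliminary Studies). On timing, the Recruitment section says "each wave of recruitment will take place over 3 months (30 PLWH and 105 alters enrolled and surveyed per month"; the three months of group sessions follow.

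**The concern.** Randomising PLWH balances the PLWH. It protects a comparison of their alters only if the alters' enrolment and baseline data cannot depend on the arm. Aim 1's primary outcomes are measured in alters, and HIV testing and condomless sex are the alters' own reports. HIV testing is also restricted to alters of negative or unknown serostatus, so who enrols sets the denominator of that outcome.

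The plan accepts the principle: it conceals the sequence and draws alters at random. If the envelope is opened before the alters have enrolled, both safeguards stop short of the people on whom these outcomes are measured. Concealment lost at that stage cannot be restored in the analysis.

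**Working it through.** The plan gives no figure for this point. The check sets the steps side by side, asks what the analysis model removes, and tests whether a later envelope fits the calendar.

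**1. Order of steps**

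| Step | Where described | Relation to the envelope |
|---|---|---|
| PLWH baseline survey | Randomization | Before |
| Naming of up to seven, random draw of four, first calls | Recruitment (end of PLWH interview) | Probably before; not stated |
| Contact effort after the first calls | Recruitment | Can be after |
| Random replacement from the existing list | Recruitment | Can be after, but the choice of name is random |
| New names chosen by the PLWH | Recruitment (only four named); Preliminary Studies (alter not reached) | Can be after |
| Alter attendance, consent and baseline answers | Eligibility Criteria for Alters; Recruitment | After, on the natural reading |

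Placing alter consent at the first visit is an inference from the in-person screening and baseline visit. Nothing in the available text makes the envelope wait for alters' baselines or says that anyone contacting or interviewing alters is unaware of arm. Some pages were removed from the public text, so this silence is judged on what remains.

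**2. Which outcomes.** HIV testing and condomless sex are alter-reported (Individual-Level Outcomes). Enacted stigma is reported by the PLWH about each listed network member (Network Composition), so it does not pass through alter enrolment.

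**3. What the model removes.** The Aims 1-3 model tests timepoint by arm. On the model's scale (log odds for these binary outcomes) the contrast is

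(follow-up − baseline) in the intervention arm − (follow-up − baseline) in the control arm.

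- A stable difference s among intervention alters appears at both times: (s − s) = 0. It cancels.
- A shift r in baseline answers only, because the arm was known: (0 − r) = −r. It stays.
- Selection on behaviour that differs by t at baseline and would have faded by follow-up anyway: (0 − t) = −t. It stays.

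The documents give no value or sign for r or t.

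**4. Room for a later envelope.** A full wave is "60 PLWH and 210 alters for two cohorts at a time", and recruitment lasts 3 months, or 3 × 52/12 = 13 weeks.

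- Alter interviewing at 25-30 per week: 210/30 = 7.0 weeks to 210/25 = 8.4 weeks. Both fit within 13.
- At the stated monthly rates: 60/30 = 2.0 months for PLWH and 210/105 = 2.0 months for alters, or 8.7 weeks. This leaves 13.0 − 8.7 = 4.3 weeks before groups start.
- Less favourable assumption, PLWH enrolled evenly over all 13 weeks: 60 × 2/13 = 9.2 (15%) enrol in the last two weeks and 60 × 4/13 = 18.5 (31%) in the last four.

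The final wave has one cohort of 30 PLWH; under even enrolment the same percentages apply.

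**The case against.** The strongest reply is that the important selection steps are already protected. Naming, the random draw and the first calls fall at the end of the PLWH interview, and visits can be scheduled during those calls, so the alter list and initial agreement probably precede the envelope. Replacement from the list is random. Dedicated alter staff are planned, so the person who opens the envelope need not interview alters. No sessions run until the wave's recruitment ends, so no alter baseline is affected by the intervention itself. The interaction term removes stable differences between arms.

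Most of this stands, and it narrows the point. It does not close it. The order is probable rather than stated, the alter staff are not said to be unaware of arm, and attendance, consent, new referrals and baseline answers still come later.

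A reader might infer more than the text supports:

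- *That PLWH, alters and alter staff are all told the arm at once.* The plan says only that the interviewer opens the envelope and records the condition. Routes through PLWH referrals or alter answers need that knowledge to travel further, and the plan does not say whether it does.
- *That alters are selected wholly after allocation.* The natural reading points the other way for naming, the draw and first calls.
- *That the pilot shows such a bias,* with 35 alters enrolled from 51 intervention PLWH and 21 from 47 controls. The numbers approached in each arm are not given, so no conclusion follows.

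Incentives to choose or answer by arm may also depend on what control participants receive. The Overview describes a no-intervention control, while Recruitment, Statistical Power and Aim 4 refer to an attention control. This is a further reason why no direction can be assigned.

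**Conclusion.** The concern holds in limited form. Followed as written, the plan lets arm be known, at least to the interviewer, before alters attend and give baselines. Contact effort, attendance and consent, new PLWH-chosen referrals and baseline answers are therefore open to arm-aware influence for two of the three primary outcomes. Enacted stigma is not affected by this route.

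The conclusion rests on two things: reading the baseline survey in the Randomization section as the PLWH's own, and the absence of any masking statement in the available text. If the alters' surveys were meant to be included, one sentence would settle the timing. The size and direction of any bias cannot be derived from the documents, and none is claimed. This is worth fixing because the change is cheap and the loss cannot be repaired later.

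**What to change.** **At minimum:**

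- Complete naming, the random draw and the calls, and close each PLWH's referral list, including reserve names, before opening the envelope.
- Draw later replacements at random from that list only.
- Keep the planned alter recruitment and interview staff unaware of arm.
- State this order in the protocol, and say who is told the arm and when.

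**Preferably:** because groups start only after the recruitment wave, open each envelope once that PLWH's alters have completed baseline, or at a fixed cut-off at the end of the wave.

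**In either case:** report alter referral, contact, enrolment and baseline characteristics by arm.

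**Cost:** protocol wording and envelope timing, with no extra assessment visits. A closed list may yield fewer alters for some PLWH; the effect on the target of 736 cannot be worked out from the documents. With the later envelope, PLWH wait up to about three months and must be recontacted with their allocation, and a few may withdraw first. Late enrollers, about 9 to 18 of 60 per wave if recruitment is evenly spread, have only two to four weeks for alter baselines and may contribute fewer alters. Neither option addresses arm-aware self-report at follow-up.
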